7.7 Software

PK parameters will be derived with standard non-compartmental analysis (NCA) methods using PKanalix® version 2023 (application of the MonolixSuite™ for NCA) or any available software for the PK analysis, and the other analysis will be performed using SAS® version 9.4 or higher.

All analyzed tables, listings, and figures will be generated using SAS® Version 9.4 or higher.

8 CHANGE FROM PROTOCOL

There is no change from protocol.

9 STATISTICAL METHODS

9.1 Study Subjects

9.1.1 Disposition of Subjects and Analysis Population

For screened population, subject disposition at the end of screening and at the end of study will be summarized including the reason of termination from each study milestone. The number of screened subjects will be used as denominator for the summary of end of screening status, and the number of screening completed subjects will be used as denominator for the summary of end of study status.

The summary of subjects who included / excluded in each analysis population (i.e., Safety population and PK population) and the reason for exclusion will be provided.

9.1.2 Protocol Deviation

A full list of protocol deviations (PD) for the study will be reviewed prior to database lock, and the important protocol deviations will be identified.

Based on Safety population, the summary of protocol deviation will be provided by protocol deviation category and sub-category, with a focus on important protocol deviation. By-subject listing of all protocol deviations will be provided.

9.2 Efficacy Evaluation

9.2.1 Demographics and Baseline Characteristics

Demographic and baseline characteristics will be summarized descriptively for the safety population and the PK population. Demographic and baseline characteristics include, but are not limited to: age, sex, race, ethnicity, weight, height, body mass index (BMI), and eGFR at baseline. BMI and eGFR at baseline will be calculated according to the formula below.

- Baseline BMI (kg/m^2) = Baseline weight (kg) / [Baseline height (cm) / 100] 2
- Baseline eGFR ($\text{mL}/\text{min}/1.73\text{m}^2$) = The mean of the eGFR obtained from two screening visits

9.2.2 Medical History

Medical history will be coded using Medical Dictionary for Regulatory Activities (MedDRA) Version 25.1 or higher. Based on Safety population, the summary of medical history will be provided by System Organ Class (SOC) and Preferred Term (PT), with a focus on ongoing status. By-subject listing of all medical histories will be provided.

9.2.3 Prior and Concomitant Medication

Prior medication is defined as any medications that start and end before the first study drug administration. Concomitant medication is defined as any medications that were administered after the first study drug administration (including medications that start prior to dosing and continued after).

The WHO Drug Global (B3) Version September, 2022 or higher will be used to categorize the verbatim descriptions of medications into the Anatomic Therapeutic Chemical (ATC) classification system.

Prior and Concomitant medications will be summarized by ATC level 2 (therapeutic class) and preferred term for the Safety population. Subjects who used the same medication on multiple occasions will only be counted once in each specific category.

By-subject listing will be provided with flags to distinguish the prior and concomitant medications.

9.2.4 Extend of Exposure

Detailed information for the study drug administration will be listed by subject for the Safety population.

9.2.5 Pharmacokinetic Concentration

HM15912 serum concentrations at each nominal sampling time will be summarized by cohort and in total for the Safety population as well as PK population, and all individual data will be listed as it is reported for the Safety population.

The serum concentration-time profiles will be depicted on a linear and semi-logarithmic scale as follows:

- Individual HM15912 serum concentrations-time plots
- Overlaid individual HM15912 serum concentrations-time plots
- Mean (\pm SD) HM15912 serum concentrations-time plots

In general, concentration values that are below the limit of quantification (BLQ) will be set to zero for the purposes of PK concentration analysis, but the embedded BLQ value between 2 quantifiable concentrations or BLQ value following the last quantifiable concentration in a profile will be set to missing. If there are missing values (e.g., Not available (N/A)) in the concentration data, these will be set to missing.

9.2.6 Pharmacokinetic Parameters

PK parameter will be presented for the PK population, and all available individual data will be listed for the Safety population.

PK parameters will be calculated using the standard NCA method with the log-up linear-down method of AUC. Actual sampling times will be used for deriving PK parameters.

The following PK parameters of HM15912 will be summarized.

Table 8 PK parameters

| Parameter | Description |
|-----------------------------|--|
| Primary endpoint | |
| $AUC_{0-\infty}^*$ | Area under the serum concentration-time profile (AUC) from time zero extrapolated to infinite time |
| C_{max} | Maximum serum concentration |
| Exploratory endpoint | |
| t_{max} | Time to maximum serum concentration |
| $t_{1/2}^*$ | Elimination half-life |
| Vd/F^* | Volume of distribution |
| CL/F^* | Clearance ($CL/F = Dose / AUC_{0-\infty}$) |
| λ_z^* | First order rate constant associated with the terminal (log-linear) portion of the curve |
| AUC_{last} | AUC from time zero to the last observable concentration |
| $AUC_{\%Extrap}^*$ | Percentage of $AUC_{0-\infty}$ due to extrapolation from t_{last} to infinity |

* As data permit

To determine the apparent first-order terminal elimination constant (λ_z), linear regression will be conducted by the logarithmically scaled concentration against time. The constant λ_z and its related parameters will be flagged and excluded in the statistical analysis if data points are

less than 3 after C_{max} .

In order to comparing the exposures among cohorts, box and whisker plots of C_{max} , $AUC_{0-\infty}$ and AUC_{last} will be generated.

After Part 1, PK parameter of HM15912 from severe renal impairment group (Cohort 2) will be estimated and compared to control group (Cohort 1). A one-way analysis of variance (ANOVA) will be used to compare log transformed PK parameter. The estimates of mean difference (Cohort 2 – Cohort 1) and corresponding 90% confidence intervals (CI), as well as each exponentiation of estimates will be presented to provide the estimates of geometric mean ratio. After statistical or clinical evaluation of results from Part 1, whether to proceed to Part 2 will be further discussed.

If Part 2 is conducted, the same analysis with Part 1 will be implemented to compare of each moderate (Cohort 3) or mild (Cohort 4) renal impairment subjects and normal renal function subjects in Cohort 1. In case the demographics (weight and age) of the moderate or mild renal impairment group compared to the normal renal function group are not within the criteria specified in the protocol, it will be considered to add that demographic information as a covariate of ANOVA. If needed, further evaluation to characterize the relationship between renal function and PK parameter will be explored.

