Rationale The primary purpose of this open-label, single-dose study is to characterize the effect of renal impairment on the pharmacokinetics (PK) of HM15912 following subcutaneous (SC) administration of a single 0.5 mg/kg dose. Recent Food and Drug Administration (FDA) draft guidance; Guidance for Industry Pharmacokinetics in Patients with Impaired Renal Function-Study Design, Data Analysis, and Impact on Dosing (2020) ¹ , suggests that renal impairment studies be conducted in patients with decreased renal function for biologic drugs of which the molecular weight is less than 69 kDa, even if the drug or its active metabolite is not primarily eliminated by the kidneys. Furthermore, the guideline recommends that a PK study be conducted in subjects with renal impairment when the drug is likely to be used in patients with impaired renal function. While agency-specific requirements such as methodology for estimated glomerular filtration rate (eGFR) assessment differ, European Medicines Agency (EMA) also suggests quite similar guidance. ² HM15912 with a molecular weight of 57 kDa is intended for use in patients with short bowel syndrome (SBS). The prevalence for renal impairment in patients with SBS remain unclear, but recent study reported that 28.1% of SBS patients developed renal impairment. ³ Therefore, the present study is being conducted to evaluate whether renal impairment has an impact on PK of HM15912. Findings from this study will be used to develop dosing recommendations so that dose may be adjusted appropriately in the presence of renal impairment. This study is a staged and parallel-group study of HM15912 in subjects with severe renal impairment (eGFR < 30 mL/min/1.73m ²) and subjects without renal impairment (eGFR ≥ 90 mL/min/1.73m ²) as a control group (Part 1) and in subjects with moderate (30 mL/min/1.73m ² ≤ eGFR < 60 mL/min/1.73m ²) and mild (60 mL/min/1.73m ² ≤ eGFR < 90 mL/min/1.73m ²) renal impairment (Part 2), matched for age, body weight and, to the extent possible, for gender to control group. The study will follow a staged approach as renal excretion is minor for HM15912 based on the results from pre-clinical study. Therefore, it is proposed that effect of renal impairment on PK of HM15912 be evaluated first in the population with severe renal impairment. If the study results confirm that severe renal impairment does not alter PK to an extent that warrants dosage adjustment, no further study is warranted. If the results do not strongly support such a conclusion, Part 2 will be conducted in subjects with moderate and mild renal impairment.	

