Approximately 16 subjects will be enrolled in Part 1; 8 subjects with severe renal impairment (Cohort 2) and approximately 8 with normal renal function (Cohort 1). The 8 subjects of Cohort 2 will be recruited first. After the end of recruitment of Cohort 2, the demographics will be pooled to determine an average value for age and weight which will be used as a reference value for Cohort 1. The subjects with normal renal function in Cohort 1 will be recruited later such that each subject's age is within ± 10 years and weight is within ± 15 kg of the mean of the Cohort 2. An attempt will be made to maintain a similar male/female ratio between Cohort 1 and Cohort 2. Care will be taken when recruiting the subjects with normal renal function such that the entire group is not younger and of lower body weight than the impaired subjects.

Part 2 will be conducted if the point estimate of geometric mean ratio (GMR) of $AUC_{0-\infty}$ for the severe renal impairment group (Cohort 2) compared to the control group (Cohort 1) [REDACTED]. Based on whether the decision criterion to proceed to Part 2 is met, up to 8 subjects with moderate renal impairment (Cohort 3) and 8 subjects with mild renal impairment (Cohort 4), matched for demographic character to control group will be enrolled.

For both Parts 1 and 2, subjects who withdraw from the study for non-safety related reasons and who are considered to be non-evaluable with respect to the primary objective may be replaced at the discretion of the sponsor but the maximum number of meaningfully evaluable patients will be not more than planned 8.

Each subject will receive a single dose of either HM15912 administered SC in the abdomen on the Day 1. Blood samples will be collected from subjects to determine PK of HM15912 up to 29 days post-dose.

Subjects will be confined to the unit PK sampling and safety assessments (as specified in the Table 2). Inpatient period will be approximately 8 days, with admission to the Clinical Research Unit (CRU) on Day -1, dosing on Day 1 and discharge in the Day 8. After completion of study procedures on Day 2, if subjects request to discharge, they may be discharged from the CRU, on their desired date, at the discretion of Investigator. If subjects discharge earlier than Day 8 and based on the subject's request, Day 3, 4, 5, 6, and 7 procedures can be done in outpatient visit. These outpatient visit could be replaced to nurse home visit at the discretion of investigator.

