5.1.1. All Subjects

1. Subjects voluntarily agree to participate in this study and sign an IRB-approved informed consent prior to performing any of the Screening visit procedures.
2. Males and females ≥ 18 and ≤ 80 years of age at the Screening visit
3. Body mass index (BMI) of ≥ 17.5 to $\leq 40.0\text{kg}/\text{m}^2$
4. Female subjects must be non-pregnant and non-lactating and either surgically sterile (e.g., bilateral tubal occlusion, hysterectomy, bilateral salpingectomy, bilateral oophorectomy), or post-menopausal for ≥ 12 months. Postmenopausal status will be confirmed through testing of follicle-stimulating hormone (FSH) levels ≥ 40 IU/L at the Screening visit for amenorrheic female subjects ≤ 60 years of age.
5. Male subjects must be surgically sterile (at least 1-year post vasectomy), abstinent or if engaged in sexual relations with women of child-bearing potential, the subject and his partner must be using the following acceptable contraceptive methods from the Screening visit and for a period of 60 days after the dose of IP. Acceptable methods of contraception for males are the use of condoms together with spermicidal foam/gel/film/cream/suppository. Effective contraceptives for the female partner include: surgical sterilization (e.g., bilateral tubal occlusion, hysterectomy, bilateral salpingectomy, bilateral oophorectomy), hormonal contraception, intrauterine contraception/device or barrier methods (female condom, diaphragm, sponge, cervical cap) together with spermicidal foam/gel/film/cream/suppository. The adequacy of other methods of contraception will be assessed on a case-by-case basis by the Principal Investigator.

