5.1.2. Additional Inclusion Criteria for Subjects with Normal Renal Function (Cohort 1)

1. No clinically relevant abnormalities identified by a detailed medical history, full physical examination, including BP and heart rate measurement, 12 -lead ECG and clinical laboratory tests.
2. Normal renal function ($\text{eGFR} \geq 90 \text{ mL/min}/1.73\text{m}^2$) at Screening based on the CKD-EPI equation.
3. Demographically comparable to the group of subjects with impaired renal function.

- A. The body weight of each subject will be within $\pm 15\text{kg}$ of the mean body weight of the severe renal impairment group (Cohort 2).
- B. The age of each subject will be within ± 10 years of the mean age of the severe renal impairment group (Cohort 2).
- C. Attempts will be made to ensure that the male-to-female distribution in Cohort 1 is comparable to that in Cohort 2; cohorts cannot comprise entirely of any one gender
- D. Other demographic characteristics, such as race and ethnicity, matched as closely as possible to the renal impairment cohort

5.1.3. Additional Inclusion Criteria for Subjects with Impaired Renal Function (Cohort 2, Cohort 3 [if applicable] and Cohort 4 [if applicable])

- 1. Good general health commensurate with the population with chronic kidney disease (renal impairment). “Health” is defined as no clinically relevant abnormalities identified by a detailed medical history, full physical examination, measurement of heart rate and 12-lead ECG as well as clinical laboratory tests (except serum creatinine and eGFR). Hypertension, diabetes mellitus, hyperparathyroidism, ischemic heart disease and other common co-morbidities in this population are possible exemptions, as long as, in the opinion of the investigator, the subject is medically stable, is on a stable drug regimen and can abide by the meals and dietary restrictions.
- 2. Meet the following eGFR criteria during the screening period based on the CKD-EPI equation:
 - A. Severe renal impairment: $\text{eGFR} < 30 \text{ mL/min}/1.73\text{m}^2$, but not requiring hemodialysis.
 - B. Moderate renal impairment (Part 2 only): $30 \text{ mL/min}/1.73\text{m}^2 \leq \text{eGFR} < 60 \text{ mL/min}/1.73\text{m}^2$
 - C. Mild renal impairment (Part 2 only): $60 \text{ mL/min}/1.73\text{m}^2 \leq \text{eGFR} < 90 \text{ mL/min}/1.73\text{m}^2$
 - D. The difference of eGFR values obtained from the two screening visits should not be more than 25%

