If Part 2 is conducted, same analysis with Part 1 will be implemented to compare of each moderate (Cohort 3) or mild (Cohort 4) renal impairment subjects and normal renal function subjects in Cohort 1. In case the demographics of the moderate or mild renal impairment group compared to the normal renal function group are not within the criteria specified in the protocol, it will be considered to add that demographic information as a covariate of ANOVA. If needed, further evaluation to characterize the relationship between renal function and PK parameter will be explored.

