1 INTRODUCTION

This Statistical Analysis Plan (SAP) has been developed based on following study documents:

- Protocol: Version 1.0 (05 Aug 2022)
- Protocol Clarification Letter (05 Sep 2022, 18 Nov 2022, and 27 Jun 2023)
- Electronic Case Report Form (eCRF): Version 2.0 (06 Jan 2023)

This SAP describes the statistical analysis to be conducted for the above mentioned protocol, and has been developed and finalized prior to database lock of the clinical database.

This SAP is being written with consideration of the recommendations outlined in the most recent International Conference on Harmonisation (ICH) E9 Guideline entitled “Guidance for Industry: Statistical Principles for Clinical Trials”, the most recent ICH E9(R1) Guideline entitled “Addendum on Estimands and Sensitivity Analysis in Clinical Trials” and the most recent ICH E3 Guideline entitled “Guidance for Industry: Structure and Content of Clinical Study Reports”.

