3.3 Analysis Schedule

After all subjects in Cohort 1 and Cohort 2 have completed all scheduled procedures, preliminary analysis will be conducted to decide whether to proceed to Part 2, or not. Part 2 will be conducted if the point estimate of GMR of $AUC_{0-\infty}$ for the severe renal impairment group (Cohort 2) compared to the control group (Cohort 1) [REDACTED]

If the decision criterion to proceed to Part 2 is met, final analysis will be conducted after all subjects who are enrolled in the Part 2 complete or discontinue the study. However, if the decision criterion to proceed to Part 2 is not met, final analysis will be conducted follow up with preliminary analysis.

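### Does leaving open whether the Part 2 demographic limits apply per subject or per cohort mean leave the reported GMR undetermined?

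*SAP*

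**What the plan says.** Protocol section 1.1 describes the Part 2 cohorts as "matched for age, body weight and, to the extent possible, for gender to control group". Section 4.1 says that Cohorts 3 and 4 "matched for demographic character to control group will be enrolled". Neither place gives a number. The numeric limits stand in sections 4.1 and 5.1.2: each Cohort 1 subject must be within 10 years and 15 kg of the Cohort 2 mean. Section 5.1.3, which covers the impaired cohorts, adds no such limit. What binds Cohorts 3 and 4 numerically is section 5.1.1: "Males and females ≥ 18 and ≤ 80 years of age at the Screening visit", and BMI from 17.5 to 40.

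For the analysis, SAP section 9.2.6 applies the Part 1 method to each Part 2 comparison. If the groups' weight and age "are not within the criteria specified in the protocol, it will be considered to add that demographic information as a covariate of ANOVA" (Protocol section 9.4.2 and the synopsis carry the same rule). SAP section 6.1.3 names the GMR with its 90% interval as the summary for every impaired cohort against Cohort 1. The code in SAP section 11 has cohort as its only effect and one contrast, severe against normal. Under SAP section 3.3, once Cohorts 1 and 2 are complete, "preliminary analysis will be conducted to decide whether to proceed to Part 2, or not".

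**The concern.** The trigger points to criteria that were not written for the comparison it governs. A reader who carries over 15 kg and 10 years must still choose the unit. Per subject, one heavy or old participant is enough to fire it; on cohort means, the averages must differ by more than the limit.

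The action is also discretionary. Nothing says when the decision is taken or whether an adjusted GMR replaces the unadjusted one or sits beside it. By then the Cohort 1 results are known and the study is open-label. The cohorts are not randomised, there are eight subjects in each, and the GMRs are meant to inform dosing recommendations. If two fair readings of one sentence led to materially different ratios, the plan would not fix its own result for Part 2.

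**Working it through.** **The plan's own precision.** Inputs from SAP section 4: 8 per cohort, SD 0.257 on the log scale. Half-width = t(0.95, 14 df) × SD × √(2/8) = 1.761 × 0.257 × 0.5 = 0.2263, interval exp(±0.2263) = 0.797 to 1.254. The SAP gives 0.2260 and 0.798 to 1.254; rounding of the SD explains the gap. This is the unadjusted model.

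**The readings can disagree.** Take Cohort 1 weights 70, 74, 78, 80, 80, 82, 86, 90 (mean 80) and Cohort 3 weights 60, 72, 76, 80, 82, 84, 86, 100 (mean 80). Two Cohort 3 subjects are 20 kg from the Cohort 1 mean, so the per-subject reading fires; the means differ by 0, so the other does not. Disagreement runs one way only, because a mean difference beyond the limit forces at least one subject beyond it.

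**How often, with no matching.** The documents give no demographic spreads. Assume weight SD 12 kg and age SD 8 years, identical populations, all cohorts drawn freely.
- Per subject: P(one subject beyond 15 kg of the Cohort 1 mean) = 2 × [1 − Φ(15 / (12 × √1.125))] = 0.24, and the same for age (10 / 8 = 15 / 12). Treating the 16 checks as independent, 1 − 0.76^16 = 98.7%.
- Cohort means: SD of the difference = 12 × √(2/8) = 6 kg, so 2 × [1 − Φ(15/6)] = 1.2% per variable, about 2.5% for either.

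Simulation with Cohort 1 held to its limits gives 98% and 1.5%, with disagreement in 97% of trials. Over weight SDs of 8 to 20 kg and age SDs of 5 to 12 years, disagreement is about 65% to 97%.

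**How often, with matching.** Those figures draw Cohort 3 freely, although the protocol calls for matching. If Cohort 3 meets the Cohort 1 limits around the Cohort 2 mean, disagreement is about 52% (30% to 62% over SDs of 8 kg/5 years to 18 kg/12 years). If every Cohort 3 subject is held within the limits of the Cohort 1 mean, it is 0% by construction.

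**When it would change the answer.** Disagreement matters only if the two models also give different ratios. Dosing is per kg, so with CL/F proportional to weight^b, log AUC varies as (1 − b) × log weight. Assume a true GMR of 1.0, no age effect and residual SD 0.257. Joint frequency of disagreement and a GMR difference above 10% (ANCOVA on log weight and age against ANOVA, SD 12 kg/8 years):

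| Cohort 3 | Joint frequency |
|---|---|
| Cohort 1-type limits, same population | 6–7% |
| Unmatched, same population | 10–14% |
| Unmatched, population 15 kg heavier | 13% (b = 1) to 18% (b = 0.5) |

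At b = 1 neither covariate has any effect, so those shifts are noise from fitting two covariates to 16 subjects.

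**Error if nothing is adjusted.** With identical populations both models cover at about 90%. With a 15-kg population gap the unadjusted model covers at 84% (GMR 1.09) for b = 0.5, 88% (1.04) for b = 0.75 and 90% (1.00) for b = 1. If a whole cohort sat 15 kg from an 80-kg control mean, the bias at b = 0.5 would be (95/80)^0.5 − 1 = +9.0% or (65/80)^0.5 − 1 = −9.9%.

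**Cost of adjusting.** In the same simulations the adjusted half-width is 0.25 with no gap and 0.32 with a 15-kg gap, against 0.22 to 0.23 unadjusted.

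**The case for a change.** The strongest case for acting is that the rule cites limits that do not exist for Cohorts 3 and 4, leaves the action to discretion, and can be applied after Cohort 1 results are in. Naming the unit, the reference mean and the leading estimate would take a sentence and no new data. The SAP lists three clarification letters among its sources, yet it adds only the words weight and age to the protocol's rule and declares no change from the protocol.

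The textual part of this stands. Three points limit its force.
- A primary estimate is named by default: the Part 2 analysis is the Part 1 analysis, which has no covariate, and the code agrees. The open question arises only once a covariate is added.
- The sentence compares one group with another, which favours the cohort-mean reading. A trigger that fires in 98% of trials with identical populations is a poor rival.
- Knowing the Cohort 1 concentrations does not show which way adjustment would move a Cohort 3 ratio, and the trigger itself depends on demographics alone.

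A binding weight and age limit for Cohorts 3 and 4 would remove the ambiguity but narrow recruitment. Making the adjusted model primary would protect against a real gap but widen the interval. Both are design choices on which sponsors may reasonably differ. The missing Part 2 contrasts in the code follow directly from the text.

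**Conclusion.** No change to the plan follows. This is missing detail in a conditional part of the study, and a competent analyst would fill it sensibly: lead with the unadjusted ANOVA, compare the groups' mean weight and age, and show a covariate model beside it if they differ markedly. The Part 1 comparison is untouched.

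The readings can disagree, in about half of trials under Cohort 1-type limits and about 97% without matching. Disagreement that coincides with a GMR difference above 10% arises in about 6% to 18% of trials. The documents show no wrong result, no hypothesis is tested, and coverage stays near 90% when the populations are comparable. It falls only if the populations differ in weight and clearance rises less than in proportion to weight.

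All trigger and coverage figures rest on assumed demographic spreads, weight exponents and population gaps; only the SD of 0.257 and the cohort size come from the SAP. The criterion for opening Part 2 is redacted and the clarification letters were not available, so the point may already be settled. If Part 2 opens, recording the unit and the leading estimate before any Cohort 3 or 4 PK result is seen would be good practice.
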